**Table 25: Summary of Primary Analysis**

Variable	Model	Population	Factors	Primary /Sensitivity	Imputation technique /algorithm
The Change from baseline in 6MWD	MMRM	ITT	Treatment Group, Visit, Treat*Visit Prostanoid Usage and Baseline 6MWD	Primary	No Imputation
The Change from baseline in 6MWD	MMRM	PP & mITT	Treatment Group, Visit, Treat*Visit Prostanoid Usage and Baseline 6MWD	Sensitivity	No Imputation
The Change from baseline in 6MWD	ANCOVA at week 18	ITT	Treatment Group, Prostanoid Usage and Baseline 6MWD	Sensitivity	LOCF and Worst value to all subjects who withdraw prematurely due to AE or death
The Change from baseline in 6MWD	ANCOVA at week 18	ITT	Treatment Group, Prostanoid Usage and Baseline 6MWD	Sensitivity	Worst case Imputation Approach (I, II & III)
The Change from baseline in 6MWD	ANCOVA at week 18	ITT	Treatment Group, Prostanoid Usage and Baseline 6MWD	Sensitivity	No Imputation
Change from Baseline in 6MWD	MMRM	ITT (all subjects completed 18 weeks of treatment)	Treatment Group, Visit, Treat*Visit Prostanoid Usage and Baseline 6MWD	Sensitivity	No Imputation
Change from Baseline in 6MWD	MMRM	mITT (all subjects completed 18 weeks of treatment)	Treatment Group, Visit, Treat*Visit Prostanoid Usage and Baseline 6MWD	Sensitivity	No Imputation
Change from baseline (defined as week 1 assessment) in 6MWD analyzed using the same	MMRM	ITT	Treatment Group, Visit, Treat*Visit Prostanoid Usage and Baseline 6MWD	Sensitivity	No Imputation

Variable	Model	Population	Factors	Primary /Sensitivity	Imputation technique /algorithm
model as primary.					
Change from baseline in 6MWD for subjects with PAH SPECIFIC THERAPIES (PHST) [PHST] and algorithm to filter the Prostacyclin IV and Oral therapy.	MMRM	ITT (all subjects on IV/SC prostacyclin +/- orals)	Treatment Group, Visit, Treat*Visit Prostanoid Usage and Baseline 6MWD	Sensitivity	No imputation
Change from baseline in 6MWD for subjects with PAH SPECIFIC THERAPIES (PHST) [PHST] and algorithm to filter for oral treatments.	MMRM	ITT (all subjects on one oral treatment of either prostacyclin or Endothelin Receptor Antagonists (ERAs) or Phosphodies terase Inhibitors (PDE 5 Inhibitors)	Treatment Group, Visit, Treat*Visit Prostanoid Usage and Baseline 6MWD	Sensitivity	No imputation
Change from baseline in 6MWD for subjects with with PAH SPECIFIC THERAPIES (PHST) [PHST] and algorithm to filter for oral treatments.	MMRM	ITT (all subjects on at least two oral treatment of either prostacyclin or Endothelin Receptor Antagonists (ERAs) or Phosphodies terase Inhibitors	Treatment Group, Visit, Treat*Visit Prostanoid Usage and Baseline 6MWD	Sensitivity	No imputation

Variable	Model	Population	Factors	Primary /Sensitivity	Imputation technique /algorithm
		(PDE 5 Inhibitors)			
Change from baseline in 6MWD ranks analyzed using same model as primary.	MMRM	ITT	Treatment Group, Visit, Treat*Visit Prostanoid Usage and Baseline 6MWD	Sensitivity	No Imputation
Responder for patients achieving $\geq 30$ meters 6MWD from baseline at Week 18	Proportion s test	ITT	Treatment	Sensitivity	NA

For open label period of study change in 6MWD at month 4, 8 and 12 from baseline (week 2) and week 18 will be analysed for all subjects participated in open label and summarized separately for subjects who switched from placebo to active treatment.

Change in 6MWD at week 18, during blinded period, from baseline will be analyse for subjects who completed 6 months and 12 months of study treatment using mITT population.

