25. Any subject who has been enrolled in any previous clinical study with inhaled NO administered through pulse delivery.

Additional Criteria to Continue to Treatment Phase from Run-in period (Week 0 to Week 2)

1. Subjects must demonstrate an average daily usage of the INOpulse device of ≥ 12 hours (rounded to the nearest hour), with no more than 2 days of usage < 8 hours per day, during the initial 2 weeks of study.
2. If a subject experiences clinical worsening during the Screening or Run-in period, the subject will not be eligible to enter into the treatment phase of the study.
3. Subjects who have been randomized at baseline and found not to meet all Inclusion criteria and/or who meet Exclusion criteria during the Run-in period will be withdrawn from the study. These subjects will be replaced to meet total target enrollment.

Part 2 Open Label Period: Diagnosis and main criteria for inclusion and exclusion:

Inclusion Criteria Part 2:

1. Informed Consent Form prior to the initiation of any study mandated procedures or assessments
2. Subject must have completed 18 weeks of blinded therapy and all assessments at week 18
3. In the opinion of the Investigator, open label treatment is in the best interest of the subject after 18 weeks of blinded treatment is completed

Exclusion Criteria Part 2 Open Label Period:

1. Subject has initiated therapy with Riociguat

Investigational product, dosage and mode of administration:

Part 1 Blinded Treatment Period:

In a randomized, double-blind manner, all subjects randomized to iNO at a dose setting of 75 mcg/kg IBW/hr will be treated by means of an INOpulse delivery device and product-specific cannula. The active study drug, nitric oxide for inhalation (iNO), will be provided in size 0.074 liter aluminum cartridge at a concentration of 6.0 mg/L (4880 ppm). All subjects will change cartridges approximately every 12 hours.

All subjects randomized to receive iNO will receive 15 mcg/kg IBW/hr for the first 2 weeks (Run-in phase) followed by iNO at 75 mcg/kg IBW/hr for 16 weeks.

Part 2 Open Label Period:

All subjects enrolled in Part 2 Open label treatment will receive iNO at 75 mcg/kg IBW/hr.

Duration of treatment:

Part 1 Blinded Treatment Period:

Until the subject has completed 18 weeks of blinded treatment

Part 2 Open Label Period:

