3. In the opinion of the Investigator open label treatment is in the best interest of the subject after one year of blinded treatment is completed or at the time the last patient is randomized

Exclusion Criteria Part 2 Open Label Period:

1. Subject has initiated therapy with riociguat

10. SUBJECT DISCONTINUATION, WITHDRAWAL AND TERMINATION FROM THE STUDY, SUBJECT REPLACEMENT, AND PROTOCOL DEVIATION CRITERIA

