**Table 1: Dosing Assignments for Run-in, Treatment Periods and Open Label**

Cohort	Part I Blinded Treatment Period		Part II Open Label
	Run-in Period Week 0 to Week 2	Treatment Period Week 3 to Week 18	Open Label Treatment
Cohort 1: Placebo	Placebo at a dose setting of 15 mcg/kg IBW/hr	Placebo at a dose setting of 75 mcg/kg IBW/hr	iNO 75 mcg/kg IBW/hr
Cohort 2: iNO 75	iNO 15 mcg/kg IBW/hr	iNO 75 mcg/kg IBW/hr	iNO 75 mcg/kg

	Part I Blinded Treatment Period		Part II Open Label
Cohort	Run-in Period Week 0 to Week 2	Treatment Period Week 3 to Week 18	Open Label Treatment
mcg/kg IBW/hr			IBW/hr

Note: Study drug is dosed according to IBW and not actual body weight. IBW is determined by a subject's sex and height, and therefore will not change during the study period.

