## 5.0 Study Design

### 5.1 General Design and Plan

[figure not shown]
This is a multi-center, randomized, double-blind, placebo-controlled, parallel-group design to determine the efficacy, safety and tolerability of pulsed iNO versus placebo in symptomatic subjects with PAH currently receiving background PAH medication and LTOT.

The study consists of two parts Part 1, the Blinded Treatment Period, and Part 2, the Open Label Extension Period. The duration of treatment in double blind period will be a maximum of 18 weeks. Subjects will be offered open label therapy when a subject completes 18 weeks of blinded drug therapy.

Screen failures will be defined as subjects who sign the ICF but fail to meet the eligibility criteria and/or do not qualify for randomization.

Subjects who do not complete their scheduled visits, have not died, and have not officially withdrawn from the study are considered lost to follow-up.

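### SAP 7.3.1 plans a Week 18 6MWD analysis in subjects completing 6 and 12 months of treatment, a subset that only later open-label participation can form; delete it or label it descriptive (minor)

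*SAP*

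**What the plan says.** The sentence closes SAP 7.3.1, after Table 25. The change in 6MWD at Week 18 of the blinded period "will be analyse for subjects who completed 6 months and 12 months of study treatment using mITT population". It gives no model, contrast or test and no statement of role, and it has no row in Table 24 or Table 25.

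The design it must fit is as follows.

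- **Blinded period.** SAP 5.1: "The duration of treatment in double blind period will be a maximum of 18 weeks".
- **Treatment afterwards.** In SAP Table 1, both cohorts receive iNO 75 mcg/kg IBW/hr in Part II. Former placebo subjects start iNO there, and former iNO subjects continue it.
- **Entry to Part 2.** Part 2 is offered, not compulsory. The protocol synopsis sets two conditions beyond consent: "Subject must have completed 18 weeks of blinded therapy and all assessments at week 18", and an investigator's opinion that "open label treatment is in the best interest of the subject after 18 weeks of blinded treatment is completed". A subject who has started riociguat is excluded.
- **Analysis set.** SAP 7.1.4 limits mITT to subjects still eligible after run-in whose average device usage exceeds 12 hours.

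**The concern.** Completing 6 or 12 months of treatment looks like a property of the blinded trial, but under the current design it cannot be. The sentence takes an outcome measured at Week 18 under blinding and restricts it to subjects selected by what happened afterwards.

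Selection has several steps: the subject's choice to enter Part 2, the investigator's judgement, a riociguat start, and staying on open-label iNO long enough. The first two can be influenced by how the subject walked at Week 18. Later retention can also differ by original arm, because one group is starting the drug and the other is continuing it. The mITT usage condition adds a second filter applied after randomisation.

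The arms of such a subset are no longer protected by randomisation. A table of Week 18 results for 6- and 12-month completers could be taken as controlled evidence of lasting benefit on the primary variable, which the uncontrolled Part 2 cannot supply.

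**Working it through.** **1. Timeline.** The sentence states no figure to reproduce, so the first check is whether the subset can exist within the blinded period.

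- 6 months = 365.25/14 = 26.1 weeks; 26.1 − 18 = 8.1 weeks into Part 2.
- 12 months = 365.25/7 = 52.2 weeks; 52.2 − 18 = 34.2 weeks into Part 2.

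This counts from randomisation. If the clock starts at Part 2 entry, the cut-offs fall 26.1 and 52.2 weeks into Part 2. Neither reading keeps the condition inside the blinded 18 weeks, and the SAP does not say which applies. The Part 2 clinic visits with a walk test are at Weeks 16, 32 and 52, so the 6-month cut (8.1 or 26.1 weeks) matches no visit.

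**2. Possible source of the sentence.** The protocol gives the investigator-opinion criterion for Part 2 twice. The synopsis refers to 18 weeks of blinded treatment. The Part 2 inclusion criteria printed in Protocol 9.4 say "after one year of blinded treatment is completed or at the time the last patient is randomized". A 6- and 12-month completer analysis would fit a blinded period of that length, so the SAP sentence may be text carried over from it. That is an inference.

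**3. What selection could do.** These calculations are illustrative.

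- Inputs from the plan: SD of change 50 to 75 m and a smallest effect of 30 m (Protocol 16.2). SAP Table 22 confirms the scale: 30 / (75 × √(4/75)) = 30/17.32 = 1.732, its interim Z for that case.
- Assumptions: Week 18 change is normal in each arm. The probability of continuing follows logit(p) = a + ln(OR) × change/SD, where OR, the odds ratio of continuing per SD of Week 18 change, is 1 to 3. The intercept a is set to give overall retention of 60 to 90% (across both arms for a common rule, within each arm otherwise).

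Difference (iNO minus placebo) among those retained:

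| Retention rule | SD | True 0 m | True 30 m |
|---|---|---|---|
| Same rule, OR 2, 81% kept | 50 | 0 | 28.1 |
| Same rule, OR 3, 60% kept | 50 | 0 | 24.6 |
| iNO OR 2, placebo OR 1, 81% kept in each | 50 | +6 | 36 |
| Placebo OR 2, iNO OR 1, 81% kept in each | 50 | −6 | 24 |
| OR 2 in both, 90% placebo and 70% iNO kept | 50 | +6 | 36 |
| OR 2 in both, 70% placebo and 90% iNO kept | 50 | −6 | 24 |
| iNO OR 3, placebo OR 1, 60% kept in each | 75 | +27 | 57 |
| Placebo OR 3, iNO OR 1, 60% kept in each | 75 | −27 | 3.5 |

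With OR = 1 in both arms there is no bias at all. Swapping the two arms' rules reverses the sign, and nothing in the documents fixes OR or retention in either arm.

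**4. Precision.** Take 150 Week 18 completers. Assume 81% enter Part 2 (the extension uptake reported for the phase 2 study, used only as an illustration) and 70 to 100% of these stay. The subset is then 150 × 0.81 = 122 down to 122 × 0.70 = 85. The 95% half-width is 1.96 × SD × √(4/n):

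| n | SD 50 | SD 75 |
|---|---|---|
| 150 | 16.0 m | 24.0 m |
| 122 | 17.7 m | 26.6 m |
| 85 | 21.3 m | 31.9 m |

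The subset is thus also less precise than the unrestricted Week 18 analysis.

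**The case against.** The strongest reply is that the sentence decides nothing. The primary analysis is the MMRM on ITT, and the gatekeeping sequence in SAP 7.5 is 6MWD, TTCW, then WHO Functional Class. The 6- and 12-month analysis carries no alpha and no decision. The sentence does not even say that the arms will be compared. All of this stands and limits the weight of the point.

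A reader might go further and infer that the subset must favour iNO, because an iNO subject who has declined has reason to stop while a placebo subject who has declined is only starting the drug. The documents do not support that direction. Protocol 8.3 keeps subjects, investigators and sponsor blinded until the last subject completes 18 weeks, so the decision to enter Part 2 is planned to be made without knowledge of the arm. For a given Week 18 result, the entry rule is then the same in both arms. Under a common rule the bias is zero when there is no effect, and a true effect is attenuated.

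The blind does not remove the problem. Retention after entry can still differ by original arm, through tolerability, response after the switch, or unblinding once the last subject has finished. Such differences could push the result either way.

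**Conclusion.** The sentence does not fit the current design. Its subset can be formed only from later Part 2 participation, so membership is settled after Week 18 and can depend on the Week 18 result and on the original arm. A treatment comparison in it is open to selection bias of unknown direction and size.

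The metre figures above rest entirely on assumed retention behaviour. They show that a distortion comparable with the 30 m planning effect is possible; they do not estimate one. Two stronger readings are not supported: that the analysis is known to be biased in favour of iNO, and that the trial's Week 18 evidence as a whole is restricted to this subset. The restriction applies to one supplementary analysis.

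Severity: minor.

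**What to change.** Delete the sentence from SAP 7.3.1. Little is lost:

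- Table 25 already lists Week 18 analyses in mITT and in subjects who complete 18 weeks, in both ITT and mITT.
- SAP 7.3.1 already plans Part 2 changes at Months 4, 8 and 12 from both Week 2 and Week 18, "summarized separately for subjects who switched from placebo to active treatment".

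If the sponsor wishes to keep the analysis, the SAP should state whether 6 and 12 months run from randomisation or from Part 2 entry, label the result descriptive, report the number of subjects remaining from each original arm, and say that it supports no treatment comparison.

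The two versions of the Part 2 investigator-opinion criterion, in the protocol synopsis and Protocol 9.4, should be reconciled at the same time.

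The cost is wording only. No data collection, sample size or confirmatory analysis changes.

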## 7.4 Secondary Analysis

All secondary analysis will be performed on ITT analysis set. All missing data will be imputed using Last Observation Carried Forward Rule (LOCF).

For all secondary continuous endpoints if normality assumptions fail then log transformed analysis will be performed. If the normality assumptions still fail, then analysis will be performed on the ranked data.

### 7.4.1 Time (in days) to First Clinical Worsening Event (TTCW)

Time to First Clinical worsening event from baseline to week 18 will be analyzed with log-rank test stratified by the prostanoid usage status (Table 26) for blinded period of study. All Individual criteria's to be analyzed using the same model as TTCW.

The censoring time points for the analyses include the time points at which subjects drop out of the study or complete the study blinded treatment period (week 18) without any of the specified events.

Time (in days) to first clinical worsening (TTCW) will be defined as time from randomization to either of the below mentioned events:

- i. Death (all-cause mortality)
- ii. Atrial septostomy

- iii. Hospitalization due to worsening of PAH (adjudicated)
- iv. Start of new specific PAH treatment (endothelin receptor antagonists [ERAs], phosphodiesterase type-5 [PDE-5] inhibitors or prostanoids), an increase in the dose of an ERA or PDE-5, increase in the dose or frequency of an inhaled prostanoids, or an increase in the dose of an intravenous or subcutaneous prostanoids by >10%.
- v. Decrease of >15% from baseline or >30% compared with the last study related measurement in 6MWD should be confirmed by a repeat measurement performed at least 14 days later
- vi. Worsening of WHO Functional Class (e.g., from Class II to Class III or IV, OR Class III to Class IV); and should be confirmed by a repeat assessment at least 14 days later

Patients who did not experience clinical worsening at the time of statistical analysis will be censored at the time of subject's last visit in part I phase, this includes patients who are lost to follow-up or have withdrawn consent.

Time to first clinical worsening (TTCW) Calculation:

1. Always calculated from date of randomization
2. If a patient discontinues study treatment prior to any of the above mentioned events then patient's last visit will be considered for censoring.
3. Patients who have not experienced TTCW will be censored at the last evaluable assessment. This includes patients who are lost to follow up or have withdrawn consent.
4. If a patient has no evaluable baseline assessment then TTCW will be censored at 0 days.
5. If a patient has no evaluable post baseline assessment then TTCW will be censored at 0 days.
6. Censoring variables for each of the individual criteria's will same as above.

TTCW will be analyzed using log rank test stratified by prostanoid usage status. The following SAS code will be used for analysis:

### Hypothesis:

The hypothesis to be tested is as follows;

$H_0: S_1(t) = S_2(t)$  versus  $H_1: S_1(t) > S_2(t)$  for at least one realization.

Where,  $S_1(t)$ : Survival Function for iNO 75 mcg/kg IBW/hr ;  $S_2(t)$ : Survival Function for matching Placebo

The following SAS code will be used for analysis:

```
PROC LIFETEST Data = TTCW notable;
  TIME Days*Censor (0);
  STRATA PROSSTATUS/GROUP = TREAT;
RUN;
```

**Missing Data:** Please refer to Section 6.3 for missing data imputation. Missing values will be imputed using the LOCF.

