7.1.2. Secondary Endpoints

The secondary endpoints include:

1. TTCW, the time (in days) from start of treatment to first event (first day the event is noted), with iNO as compared to placebo, measured from baseline to 18 weeks. TTCW event is defined as any of the following:
 - a. Death (all-cause mortality)
 - b. Atrial septostomy
 - c. Hospitalization due to worsening of PAH (adjudicated)
 - d. Start of new specific PAH treatment (endothelin receptor antagonists [ERAs], phosphodiesterase type-5 [PDE-5] inhibitors or prostanoids), an increase in the dose of an ERA or PDE-5, increase in the dose or frequency of an inhaled prostanoids, or an increase in the dose of an intravenous or subcutaneous prostanoids by >10%.
 - e. Decrease of >15% from baseline or >30% compared with the last study related measurement in 6MWD should be confirmed by a repeat measurement performed at least 14 days later
 - f. Worsening of WHO Functional Class (e.g., from Class II to Class III or IV, OR Class III to Class IV); and should be confirmed by a repeat assessment at least 14 days later
2. Change in WHO Functional Class, with iNO as compared to placebo, from baseline to 18 weeks

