16.3.2. Secondary Efficacy Endpoints

The secondary efficacy endpoints include:

1. TTCW*: The time (in days) from start of treatment to first event (first day the event is noted), with iNO as compared to placebo, measured from baseline to week 18. TTCW event is defined as any of the following:
 - a. Death (all-cause mortality)
 - b. Atrial septostomy
 - c. Hospitalization due to worsening of PAH (adjudicated)
 - d. Start of new specific PAH treatment (endothelin receptor antagonists [ERAs], phosphodiesterase type-5 [PDE-5] inhibitors or prostanoids), an increase in the dose of an ERA or PDE-5, increase in the dose or frequency of an inhaled prostanoids, or an increase in the dose of an intravenous or subcutaneous prostanoids by >10%.
 - e. Decrease of >15% from baseline or > 30% compared with the last study related measurement in 6MWD and should be confirmed by a repeat measurement performed at least 14 days later
 - f. Worsening of WHO Functional Class (e.g., from Class II to Class III or IV, OR Class III to Class IV); and should be confirmed by a repeat assessment at least 14 days later
2. Change in WHO Functional Class, with iNO as compared to placebo, from baseline to 18 weeks.

The TTCW endpoint will be analyzed with log-rank test stratified by the prostanoid usage status. The censoring time points for the analyses include the time points at which subjects drop out of the study or complete the study without any of the specified events.

The WHO Functional Class endpoint will be analyzed with the same method as that for the primary endpoint. Change from baseline to week 18 will also be evaluated as an exploratory analysis.

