#### Missing data imputation for secondary endpoint:

For all the other efficacy endpoints, the last observation carry forward (LOCF) approach will be used in handling the missing data as that used in the EARLY study ([Galiè 2008](#)).

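### SAP 7.4.1 prescribes LOCF for time to clinical worsening without saying what is imputed, which conflicts with the endpoint's censoring rules and, read literally, lets an unconfirmed last fall count as confirmed

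*SAP*

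**What the plan says.** **LOCF.** SAP 7.4.1 (under Hypothesis, after the PROC LIFETEST code) closes its account of TTCW with: "Please refer to Section 6.3 for missing data imputation. Missing values will be imputed using the LOCF". The opening of SAP 7.4 applies LOCF to all missing data in the secondary analyses. SAP 6.3 says: "For all the other efficacy endpoints, the last observation carry forward (LOCF) approach will be used", and protocol 16.3.5 has the same general rule. None of these places exempts TTCW.

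**Censoring.** SAP 7.4.1 says that patients without clinical worsening, including those lost to follow-up or withdrawing consent, "will be censored at the time of subject's last visit in part I phase". Its numbered rules add the last evaluable assessment for event-free patients, and day 0 for a patient with no evaluable post-baseline assessment. Protocol 16.3.2 says: "The censoring time points for the analyses include the time points at which subjects drop out of the study".

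**Confirmation.** A 6MWD fall (more than 15% from baseline, or more than 30% against the last study measurement) "should be confirmed by a repeat measurement performed at least 14 days later" (protocol 7.1.2). WHO class worsening needs a repeat assessment on the same terms. SAP Table 4 says only that confirmation is tied to visit-window mapping. It does not say whether an imputed value may serve as the repeat.

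**The concern.** TTCW is a censored time-to-event endpoint. A subject who leaves without an event contributes follow-up to the point of leaving and nothing after it. LOCF does the opposite: it supplies values for visits after the subject has gone. The SAP prescribes both for one endpoint and gives no order of precedence.

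Two consequences follow if the LOCF sentence is applied as written. First, follow-up can be extended beyond what was observed. Second, a low value at the last attended visit is copied to the next visit, where it can satisfy the repeat requirement that was meant to screen out single noisy results.

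TTCW stands directly after 6MWD in the gatekeeping order (protocol 16.3.4, SAP 7.5). Whether a drop-out with one low walk is an event or is censored should not be left to a programming choice that might be made after unblinding.

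**Working it through.** **1. Setting the rules side by side.** The subjects below are assumed examples.

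| Subject | Censoring rules | LOCF read literally |
|---|---|---|
| Baseline 300 m, Week 6 250 m, then drops out | One unconfirmed fall; censored at Week 6 | 250 m carried to Week 10; fall repeated; event |
| WHO class II at baseline, III at Week 6, then drops out | One unconfirmed worsening; censored | Class III carried to Week 10; event |
| No post-baseline assessment | Censored at day 0 | Baseline carried to Week 18; event-free throughout |

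In the first row the observed fall is 1 − 250/300 = 16.7%, and the carried value gives 16.7% again. The scheduled gap is Week 6 (day 42) to Week 10 (day 70), which is 28 days. Even at the edges of the efficacy windows in SAP Table 17 the gap is 63 − 49 = 14 days, so the carried value meets the interval.

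The criterion of more than 30% against the last measurement does not confirm itself this way. The carried value equals the last value, so that comparison shows a fall of 1 − 250/250 = 0%.

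**2. Number of subjects exposed.** The plan's inflation reproduces: 150/(1 − 0.20) = 187.5, so 188, and 75/0.80 = 93.75, so 94 per arm. The planned drop-out is 0.20 × 188 = 37.6, about 38 subjects.

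**3. Illustrative size for the >15% criterion.**

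From the documents: SD 50 to 75 m (protocol 16.2, used here as the SD of change) and 38 drop-outs.

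Assumed: baseline 300 m, so that 15% is 45 m; mean change 0; normal changes; visit correlation 0.5 to 0.7; last attended visit equally likely at Week 6, 10 or 14; no later assessment; the next visit taken as the repeat.

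- Probability of a fall at one visit: p = Φ(−45/SD). For SD 50, Φ(−0.9) = 0.184. For SD 75, Φ(−0.6) = 0.274.
- Probability c that a fall at one visit is also present at the next (bivariate normal). For SD 50, c = 0.421 at correlation 0.5 and 0.551 at 0.7. For SD 75, c = 0.500 and 0.619.
- LOCF converts a subject only if the last visit shows a fall and the visit before did not; otherwise the fall is already confirmed by observation. The probability is p if the last visit is Week 6, and p(1 − c) if it is Week 10 or 14. The average is p[1 + 2(1 − c)]/3.

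| SD (m) | Correlation | Average probability | × 38 |
|---|---|---|---|
| 50 | 0.5 | 0.184 × 2.158/3 = 0.132 | 5.0 |
| 50 | 0.7 | 0.184 × 1.898/3 = 0.116 | 4.4 |
| 75 | 0.5 | 0.274 × 2.000/3 = 0.183 | 6.9 |
| 75 | 0.7 | 0.274 × 1.762/3 = 0.161 | 6.1 |

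LOCF therefore adds about 4 to 7 events across the trial. If a quarter of drop-outs leave before Week 6, the range is 0.75 × 4.4 = 3.3 to 0.75 × 6.9 = 5.2.

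**4. By arm.** A separate simulation used 94 per arm and 20% random drop-out after Weeks 6 to 14. It took a mean baseline of 275 or 325 m (SD 75 m), SD of change 50 or 75 m, correlation 0.5 or 0.8, and mean change 0 on placebo and +30 m on iNO. Counting carried values as confirmation added 1.9 to 3.6 events on placebo and 0.7 to 2.3 on iNO.

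**The case against.** The strongest reply is that the LOCF line is stray generic text. The same sentence appears in SAP 7.4.2 for WHO class, where it has a clear function. The censoring rules in SAP 7.4.1 are specific and numbered, and the PROC LIFETEST code uses only a time and a censoring flag, with no visit value to impute. A careful programmer would probably censor.

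Several stronger readings are tempting and are not supported:

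- *That the SAP instructs a carried-forward value to confirm a fall.* No text says so. The requirement that a repeat be performed favours an observed one. Self-confirmation is one literal reading.
- *That all 6MWD falls confirm themselves.* The comparison with the last measurement does not.
- *That the two rules can never coexist.* LOCF could fill a visit-level component while time is still censored at the last visit. The documents do not describe this, and the LOCF line would then have no stated purpose for TTCW.
- *That every last-visit fall is an added event.* Multiplying 38 by 0.184 to 0.274 gives 7.0 to 10.4, but this includes subjects whose fall was already confirmed by two observed visits.
- *That the log-rank test is biased.* This needs the literal reading and also a difference between arms in drop-out or in falls, neither of which is shown.

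Missing repeats will also be fewer than assumed above. Subjects off drug are encouraged to continue assessments to Week 18 (protocol 10.1), and the early-termination visit includes the walk test and WHO class (protocol 11).

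These points narrow the consequence. They do not remove the conflict, because LOCF is written into the TTCW section itself.

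**Conclusion.** The point holds as a conflict between stated rules. LOCF is prescribed for TTCW in SAP 7.4.1, 7.4 and 6.3 and in protocol 16.3.5, with no statement of what is imputed. SAP 7.4.1 and protocol 16.3.2 censor instead. Those censoring rules are worded differently from one another, but none runs past observed follow-up.

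Self-confirmation is a possible consequence of literal application, limited to the >15% from baseline criterion and WHO class. It affects only subjects whose last observed visit shows a new fall and who have no later assessment.

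The figure of about 4 to 7 added events covers the >15% criterion alone. It rests on an assumed baseline, visit correlation and drop-out pattern, and on no mean change in any drop-out. A positive treatment effect or successful off-drug follow-up lowers it. The documents give no TTCW event rate to set it against. In the simulation by arm, placebo gained more events than iNO although drop-out was random, because falls were assumed rarer on iNO.

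This should be corrected before unblinding. It is a wording fault in the first gated secondary endpoint and does not touch the primary analysis.

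**What to change.** 1. Delete the LOCF sentence from SAP 7.4.1.
2. Exempt TTCW explicitly from LOCF in SAP 6.3, SAP 7.4 and protocol 16.3.5.
3. State in SAP 7.4.1 that only observed repeat assessments can confirm the 6MWD and WHO class components, and that subjects without a confirmed event are censored as SAP 7.4.1 and protocol 16.3.2 already provide.
4. Optionally, add a sensitivity analysis that counts an unconfirmed fall at the last observed visit as an event. This shows how far the result depends on missing repeats.

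The cost is a few lines in the SAP and one clause in protocol 16.3.5, with no new data collection. The downside is that a few fewer events may be counted.
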